5.1.1 Pre-screening for PD Cohorts only (NSCLC)

Participants in Part A and B NSCLC PD cohorts only must have tumor-associated as measured by a prior to completion of the remaining screening procedures. A participant is considered enrolled only when a main protocol-specific informed consent is signed. If allowed by institutional practices, sites are required to use a pre-screening consent for the staining to evaluate from biopsy samples. Participants must have a lesion that can be biopsied at an acceptable clinical risk as judged by the Investigator in order to be eligible for the NSCLC PD cohorts.

Participants in Parts A and B NSCLC PD cohorts whose pre-treatment biopsy yields inadequate tissue quantity or quality will not be eligible for NSCLC PD cohorts, but they can be enrolled in dose escalation (Part A and B) cohorts.

Participants in Part A and B NSCLC PD cohorts will be able to sign the main ICF and continue with other screening procedures while the result is available for the determination of participant eligibility in NSCLC PD cohorts.

5.1.2 Screening Period

The screening period will be up to and begins by signing of the main protocol informed consent form (ICF). The screening assessments are shown in Table 2-2.

If a participant exceeds the screening period due to a study-related procedure (eg, scheduling of a tumor biopsy or waiting for a study-related laboratory value), the participant must be re-consented but does not require a new patient identification number. In this situation, the fewest number of procedures from the initial screening should be repeated to qualify the participant, while maintaining participant safety and eligibility. Within a given disease type, participants meeting all eligibility criteria will be enrolled in the study using an Interactive Response Technology (IRT) according to the part and treatment arm availability.

5.1.3 Treatment Period

The dosing regimen of BMS-986258 is Q4W.

Refer to Section 5.1 and

All participants will be treated for up to 96 weeks. The treatment period will consist of up to 12 treatment cycles (each cycle is 8 weeks in length). Following each treatment cycle, the decision to treat a participant with additional cycles of study therapy (up to a maximum of 12 cycles) will be based on response assessment at the end of each cycle. Continuous safety evaluation and tumor assessment (every 8 weeks [Q8W]) will guide the decision to treat a participant with additional cycles of study therapy if the participant has confirmed clinical benefit (up to a maximum of 96 weeks) for all study parts.

Study visits will be performed every 2 weeks for the first 8 weeks following the first dose of study treatment for the BMS-986258 Monotherapy Escalation (Part A), BMS-986258 with rHuPH20 SC for first dose (Part A1), and BMS-986258 in Combination with Nivolumab (Part B). Study visits at Cycle 2 and beyond will be every 4 weeks. During Cycles 1 and 3 of the treatment period, additional study visits to collect samples for intensive PK, ADA, required. See Section 9.5 for further details. In Part C (BMS-986258 in

Combination with nivolumab Cohort Expansion), study visits will be performed every 2 weeks for the first cycle. Study visits at Cycle 2 and beyond will be every 4 weeks.

In Part A (BMS-986258 Monotherapy Escalation), BMS-986258 will be administered Q4W. BMS-986258 will be infused according to dosing and infusion times in Table 7.1-1. Shorter infusion times may be used for initial dose panels and longer infusion times will be used for the higher dose panels.

In Part A1 (BMS-986258 SC for first dose), BMS-986258 will be co-administered with rHuPH20 for the first dose of BMS-986258 in Cycle 1. All subsequent doses will be administered as monotherapy IV Q4W. Alternatively, participants in cohort A1 who have received SC BMS-986258 on Cycle 1 Day 1 will be offered the option to receive subsequent IV combination therapy of BMS-986258 with nivolumab (480 mg) at the highest dose of BMS-986258 that has been shown to be safe and tolerable in the dose escalation (Part B). Treatment will be given Q4W twice per cycle, for up to twelve 8-week cycles (96 weeks).

BMS-986258 SC should be administered in the abdomen or alternatively in the thigh. ENHANZE[®] Drug Product (rHuPH20) should not be injected into or around an infected or acutely inflamed area because of the danger of spreading a localized infection. Clinical judgment should be used in determining the best site for SC drug administration. Please refer to the Pharmacy Manual for dose-specific infusion times and sites of SC administration. BMS-986258 will require a observation period following the completion of the infusion for the first 2 doses for each participant.

In Part B (BMS-986258 in Combination with Nivolumab Escalation) and Part C (BMS-986258 in Combination with Nivolumab Cohort Expansion), nivolumab will be administered Q4W and will be infused over 30 minutes. When both BMS-986258 and nivolumab are given in combination, nivolumab will be given first, over 30 minutes, followed by a street observation period then BMS-986258, over approximately street BMS-986258 infusion will begin after completion of the infusion of nivolumab. BMS-986258 infusions will require observation period following the completion of the infusion for the first 2 doses for each participant. Shorter infusion times for BMS-986258 may be used for initial dose panels and longer infusion times will be used for the higher dose panels.

Please refer to the Pharmacy Manual for dose-specific infusion times and administration details for nivolumab and BMS-986258.

During dose escalation, all eligible participants will be assigned to Part A until the decision is made to escalate to the third dose cohort. Subsequently, treatment in Part B may be initiated, and dose escalation in the 2 parts will occur in parallel. The dose(s) of BMS-986258 for Part A1 will be selected based on preliminary safety and available PK and PD data. Once a dose has been determined to be safe and tolerable from Part A, Part A1 can be initiated independently, using all available safety and PK data and may be run in parallel with Parts A and B. The dose(s) of BMS-986258 monotherapy or in combination with nivolumab for Part A and B NSCLC PD

Protocol Amendment No.: 07

[figure not shown]
cohorts will be selected based on preliminary safety and available PK and PD data. The doses selected for Part C will not exceed the MTD (or MAAD if no MTD is determined) in Part B, but may incorporate assessment of other data including toxicities and PK, PD data from Parts A and B, as well as feasibility and bioavailability (BA) of SC administration from Part A1.

Sentinel Participant:

During the dose escalation phase in Part A, Part A1, and Part B, a staggered dosing (sentinel participant) approach will be used. In Part A and Part A1, the first participant to be dosed at Cycle 1 Day 1 of the first dose level will be observed for 5 days before additional participants (ie, Participant 2 onward in that cohort) receive study treatments in the same dose level. In Part B, the first participant to be dosed at Cycle 1 Day 1 of each dose level will be observed for 5 days before additional participants (ie, Participant 2 onward in that cohort) receive study treatments in the same dose level.

[figure not shown]
Initially, 3 participants will be enrolled at the start of each cohort, in accordance with the sentinel participant approach cited above. However, to allow for any unforeseen discontinuations (such as disease progression) before the 4-week DLT period (28 days) is completed, an extra participant may be enrolled in each dose escalation cohort. Therefore, there may be a total of 4 participants (3 + 1) at the start of each cohort, provided that the fourth participant is able to start dosing within approximately 1 week of the third participant in the same dose escalation cohort. Additional information on DLTs can be found in Section 7.1.1.

5.1.3.1 BMS-986258 Monotherapy Dose Escalation (Part A) (Including NSCLC PD Cohorts) and Subcutaneous Dose (Part A1)

In dose escalation, each participant will be administered IV doses of BMS-986258 in planned dose levels of 8, 24, 72, 200, 480, 800, 1200, 1600, and 2400 mg Q4W twice per cycle, for up to 12 cycles (96 weeks) of study therapy.

monotherapy dose cohorts may be in the escalation phase based upon the BLRM analysis and clinical evaluation of all available safety and PK/PD data. Participants enrolled in the NSCLC PD cohorts will receive a dose level that has already been cleared for safety within the corresponding dose escalation cohort.

clinical evaluation of all available safety and PK/PD data. Once the tolerability (during the DLT evaluation) of a dose level has been established, additional participants may be added at that dose level to better characterize the safety, PK, and PD profiles.

The dose escalation phase of the study will evaluate the safety and tolerability of BMS-986258, administered as monotherapy based on DLTs, using a BLRM (for the BMS-986258 Monotherapy Dose Escalation [Part A]). During the Monotherapy Dose Escalation phase, approximately 3 participants will be treated at each dose level. Cohort tolerability assessment and subsequent dose recommendation will occur when at least 2 evaluable participants within a cohort have completed the 4-week DLT period. Any toxicities that occur beyond the DLT period will be considered in making dose level decisions and/or dose level modifications. Additional information on DLTs can be found in Section 7.1.1.

If the potential DLT occurring in the third evaluable participant regarding any specific dose level does not influence the dose recommendation by BLRM, the next dose level may proceed without waiting for the third participant to complete the corresponding DLT observation period, after discussion and agreement between the Sponsor and investigators. Continuous reassessment of dose recommendation, by BLRM in the BMS-986258 Monotherapy Escalation (Part A) will be carried out for each dose level. Planned dose levels for dose escalation are provided in Section 5.5.

Approximately up to participants are expected to be treated in the BMS-986258 monotherapy SC cohort(s) (Part A1). Refer to Section 10 for additional details. For each participant in Part A1, BMS-986258 will be co-administered SC with rHuPH20 for the first dose in Cycle 1. All subsequent doses of BMS-986258 will be administered as monotherapy IV, Q4W twice per cycle, for up to twelve 8-week cycles (96 weeks). Alternatively, participants in cohort A1 who have received SC BMS-986258 on Cycle 1 Day 1 will be offered the option to receive subsequent IV combination therapy of BMS-986258 with nivolumab (480 mg) at the highest dose of BMS-986258 that has been shown to be safe and tolerable in the dose escalation (Part B). Treatment will be given Q4W twice per cycle, for up to twelve 8-week cycles (96 weeks).

The dose selected for Part A1 will not exceed a dose determined to be safe and tolerable in Part A.

5.1.3.2 BMS-986258 in Combination with Nivolumab Dose Escalation and NSCLC PD Cohorts (Part B)

Approximately participants are expected to be treated during the BMS-986258 combination with Nivolumab Dose Escalation (Part B) of the study guided by BLRM-copula for the primary objective. Additionally, approximately participants are expected to be treated in the NSCLC PD cohorts in Part B, with approximately up to participants per cohort, in order to obtain participants with evaluable biopsies per cohort. Refer to Section 10 for additional details. Therefore, a total of participants are expected to be treated in Part B.

Based on preliminary safety, PK, and PD from Part A, the starting dose of BMS-986258 in Part B may be higher than the starting dose from Part A. Each dose level in Part B, including the starting dose, will only be opened after at least higher dose levels in Part A have demonstrated tolerability during the DLT observation period.

. Each participant may be administered IV doses of

BMS-986258 in planned dose levels of 8, 24, 72, 200, 480, 800, 1200 and 1600 mg combined with 480 mg of nivolumab Q4W (twice per cycle), for up to twelve 8-week cycles of study therapy (96 weeks) unless criteria for study drug discontinuation are met earlier (see Protocol Section 8).

during escalation based upon the BLRM analysis and clinical evaluation of all available safety and PK/PD data. Participants enrolled in the PD cohorts will receive a dose level that has already been cleared for safety within the corresponding dose escalation cohort. Upon completion of study therapy, all participants will enter the Safety Follow-up period.

The combination dose escalation phase (Part B) of the study will evaluate the safety and tolerability of BMS-986258, given in combination with nivolumab, based on DLTs, using a BLRM-copula. During the combination dose escalation phase, approximately participants will be treated at each dose level. Cohort tolerability assessment and subsequent dose recommendation will occur when at least evaluable participants within a cohort have completed a 4-week DLT period. Any toxicities that occur beyond the DLT period will be considered in making dose level decisions and/or dose level modifications. Additional information on DLTs can be found in Section 7.1.1.

If the potential DLT occurring in the third evaluable participant regarding a/any specific dose level does not influence the dose recommendation the BLRM-copula, the next dose level may proceed without waiting for the third participant to complete the corresponding DLT observation period, after discussion and agreement between the Sponsor and investigators. Continuous re-assessment of dose recommendation, BLRM-copula in the Safety Evaluation of Combination Doses of BMS-986258 with Nivolumab (Part B), will be carried out for each dose level. Planned dose levels for dose escalation are provided in Section 5.5.

Planned dose levels may be modified, or dose levels added, based upon the BLRM-copula analysis for combination and clinical evaluation of all available safety and PK/PD data. Once the tolerability (during the DLT evaluation) of a dose level has been established, additional participants may be added at that dose level to better characterize the safety, PK, and PD profiles.

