3.3 Benefit/Risk Assessment

As of the reporting cut-off date of 12-Sep-2019, 25 participants have been treated with various doses of BMS-986258 as monotherapy (n = 3 at 8 mg, n = 3 at 24 mg, n = 4 at 72 mg, n = 4 at 200 mg, n = 4 at 480 mg, n = 4 at 800 mg, and n = 3 at 1200 mg). As of the data cutoff date of 12-Sep-2019, based on 25 participants treated with BMS-986258 IV monotherapy in doses 8 to 1200 mg, the majority of AEs observed were in severity. It reatment-related AEs were reported.

AEs were reported.

no dose-limiting toxicities (DLTs) were observed. Therefore, BMS-986258 administered as

no dose-limiting toxicities (DLTs) were observed. Therefore, BMS-986258 administered as monotherapy is considered to have a manageable safety profile in doses up to 1200 mg IV. Additionally, there are preliminary data on 4 participants who have received at least 1 cycle of BMS-986258 480 mg IV combined to nivolumab 480 mg; none of them presented a DLT during the observation period of 28 days. At this time, no efficacy data are available. There is limited prior human experience with BMS-986258; therefore, clinical benefit in participants with advanced solid tumors has not been established, but the initial data support its continued development.

Extensive details on the safety profile of nivolumab are available in the IB and will not be repeated herein.

Overall, the safety profile of nivolumab monotherapy as well as in combination with ipilimumab is manageable and generally consistent across completed and ongoing clinical trials with no MTD reached at any dose tested up to 10 mg/kg. Most AEs were low-grade with relatively few related AEs. There was no pattern in the incidence, severity, or causality of AEs with respect to nivolumab dose level. A pattern of immune-related AE (irAE) has been defined, for which management algorithms have been developed; these are provided in Appendix 8. Most high-grade events were manageable with the use of corticosteroids or hormone replacement therapy (endocrinopathies) as instructed in these algorithms. Additional details on the safety profile of nivolumab, including results from other clinical studies, are also available in the nivolumab IB.³¹

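### The Part A early-opening check tests a hypothetical DLT only in the third participant, so when an optional fourth is also still inside the DLT window one pending outcome goes untested

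*Combined protocol and SAP*

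**What the plan says.** Three statements in the protocol have to be read together.

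- **Cohort size at start** (Section 5.1.3, Sentinel Participant). The base case is three: "Initially, 3 participants will be enrolled at the start of each cohort". One extra participant may be added as cover for early discontinuation: "Therefore, there may be a total of 4 participants (3 + 1) at the start of each cohort". This extra person has to begin treatment no more than about a week after number three.
- **When the recommendation is made** (Section 5.1.3.1, Part A). "Cohort tolerability assessment and subsequent dose recommendation will occur when at least 2 evaluable participants within a cohort have completed the 4-week DLT period".
- **When the next level may open early** (Section 5.1.3.1). The condition begins "If the potential DLT occurring in the third evaluable participant regarding any specific dose level does not influence the dose recommendation by BLRM". If it is met, and the Sponsor and investigators agree, the next level can start before the third participant has finished the window. The fourth is not mentioned.

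Section 5.1.3.2 gives Part B the same condition, using the BLRM-copula: "If the potential DLT occurring in the third evaluable participant regarding a/any specific dose level does not influence the dose recommendation". The Part B completer number is not readable in the public text.

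Section 7.1.1 sets the window at 28 days. In Part A it counts as DLT evaluable anyone who receives one dose and completes the window. Nothing there leaves out a fourth participant.

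**The concern.** The check asks whether an outcome not yet known could change the model's recommendation. If it could not, waiting adds nothing and the next cohort can start. That reasoning holds only if every unknown outcome is put into the test.

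With three participants and two completers, one outcome is unknown and the check covers it fully. With four participants and two completers, two can be unknown and the check covers one. The next cohort could then be dosed at a level that the overdose-control rule would have rejected once the cohort's data were complete. This is a first-in-human study, and Section 10.1.1 presents control of overdosing as a main reason for the design.

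**Working it through.** The plan gives no figure for this rule to reproduce. The check is a count, followed by two illustrations.

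**1. Count of pending participants**

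- Dosed: 4 (Section 5.1.3). Completed: 2 (Section 5.1.3.1). Pending: 4 − 2 = 2.
- Worst case the check covers: (0 + 1) DLTs in (2 + 1) participants = 1/3.
- Worst case that can occur: (0 + 2) in (2 + 2) = 2/4.

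If the third is dosed x days after the second, the third and fourth are both pending for the x days after the second completes. The fourth then stays pending for up to about 7 more days.

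**2. Chance of the untested outcome**

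For a true DLT rate p, independent outcomes and no follow-up yet elapsed:

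| p | At least one DLT, 1 − (1 − p)² | Both, p² |
|---|---|---|
| 0.10 | 0.190 | 0.010 |
| 0.25 | 0.438 | 0.063 |
| 0.33 | 0.551 | 0.109 |

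For each p these are upper bounds, because a participant who is event-free partway through the window has less risk left.

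**3. Effect on the overdose criterion (illustration)**

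The prior, overdose threshold and cap are not readable, so all three are assumed.

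- Model: logit p(d) = log α + β·log(d/1200).
- Prior: log α normal with mean logit(0.10) and SD 2; log β normal with mean 0 and SD 1; independent.
- Overdose: p(d) > 0.33. The next dose is allowed if the posterior probability of overdose there is below 0.25.
- Data: 0 DLTs at all lower levels. Cohort sizes are those in Section 3.3 (3, 3, 4, 4, 4, 4, 3 at 8 to 1200 mg), with 3 assumed at 1600 mg.

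Posterior probability of overdose at the next dose, by grid integration:

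| Step (mg) | 0/2 | 1/3 (check as written) | 2/4 (both pending) |
|---|---|---|---|
| 480 to 800 | 0.03 | 0.20 | 0.46 |
| 800 to 1200 | 0.06 | 0.25 (0.246) | 0.51 |
| 1200 to 1600 | 0.08 | 0.31 | 0.59 |
| 1600 to 2400 | 0.11 | 0.39 | 0.69 |

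In the first two rows the check passes and 2/4 would fail. In the last two, 1/3 already exceeds 0.25, so the check as written makes the team wait.

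**4. Sensitivity to the prior**

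With a prior median of 25%, 1/3 gives 0.32, 0.37, 0.40 and 0.45 at the four steps, so the team waits at all of them. With 15%, the 800 to 1200 mg step gives 0.29 and also fails.

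A wider scan covered 324 assumed settings:

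- reference dose 800, 1200 or 2400 mg;
- prior median 0.1, 0.2 or 0.3;
- SD of log α 1.5, 2.0 or 2.5, and SD of log β 0.7 or 1.0;
- current level 72 to 1600 mg.

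The 1/3 check passed in 135, and 2/4 would have blocked 124 of those. The settings carry no weights, so these counts are not operating characteristics of the trial.

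**The case against.** **Early opening is optional and supervised.** It needs agreement between Sponsor and investigators, Section 5.1.3.1 calls for continuous reassessment, and Section 10.1.1 brings in all available data. This stands as a partial safeguard. But a pending outcome is not yet data, and the protocol chose a model-based test for that situation.

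**The fourth is only a spare.** Section 5.1.3 does describe the extra place that way. Under Section 7.1.1, though, a fourth participant who completes the window is evaluable, and a DLT in that participant would count.

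**The sentence may waive only the wait for the third.** On that reading the fourth must still be awaited and there is no gap. The text does not say so; the same edit would settle it.

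**The exposure is short.** Once the third has finished without a DLT, only the fourth is pending and the worst case is 1/4. That is milder than the 1/3 already tested (0.21 against 0.25 at 800 to 1200 mg under the same assumptions). This is right and limits the problem to the overlap.

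**The illustrated steps are in the past.** Section 3.3 reports three participants already treated at 1200 mg, and for the steps above it the check as written blocks early opening under the assumed prior. This also stands.

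**A rule may sit in redacted text.** Words are removed from a completion condition in Section 3.3.5, from Section 5.1.3.2 and from Section 10.1.1. This cannot be excluded, and it lowers confidence.

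A reader might also infer from Section 3.3 (for example "n = 4 at 480 mg, n = 4 at 800 mg") that four-participant starts are routine, since four of the seven levels (72, 200, 480 and 800 mg) had n = 4. The documents do not support that. Those are totals treated by the cut-off date, and the protocol also allows participants to be added or replaced later. Nothing shows that four started together or that early opening was used.

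**Conclusion.** The point holds for Part A as worded. When a fourth participant is dosed and both the third and fourth are pending, the check does not guarantee that their outcomes cannot overturn the recommendation. With three participants the rule is sound.

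The gap matters only where the model tolerates one DLT in three but not two in four. Under the assumed 10% prior median that is so at 480 to 800 mg and, narrowly, at 800 to 1200 mg. It is not so for the steps above 1200 mg and, with a 25% prior median, not at any step from 480 mg up.

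Three stronger conclusions are tempting but unsupported:

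- That the same failure is established in Part B. The wording matches, but without the completer number two pending participants cannot be confirmed.
- That there is an 11% risk of a wrong escalation. That figure is at most the chance that both pending participants have a DLT at a 33% true rate, and it falls as follow-up accrues.
- That participants were exposed to an overdose through this rule. Nothing readable shows this, and Section 3.3 reports no monotherapy DLTs up to 1200 mg.

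Severity is moderate. Confidence is medium, because the model's prior and limits and parts of the escalation text are redacted.

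**What to change.** Reconcile the cohort-size text in Section 5.1.3 with the early-opening sentences in Sections 5.1.3.1 and 5.1.3.2. The what-if run of the BLRM or BLRM-copula should cover every participant of the cohort still inside the DLT window, each entered as a DLT, and not only the third. Early opening would then require the recommendation to be unchanged under that run. If redacted text already handles a pending fourth participant, a cross-reference from these two sections is enough.

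The cost is one sentence in each section, one more model run when a fourth is pending, and an occasional wait of about a week for that participant. No dose level, cap or overdose threshold needs to change.
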